7.4.6	Sensitivity analyses.....	27
7.4.7	Post-hoc sensitivity analyses.....	27
7.4.8	Missing data.....	28
7.4.9	Limits of detection	28
7.4.10	Multiple testing	28
8.	Bibliography	28
9.	Amendments to the SAP	29
APPENDIX A: Skeleton tables and figures		31
Figure F1	Flow of participants	32

STATISTICAL ANALYSIS PLAN

COPTIC: Coagulation and platelet laboratory testing in cardiac surgery
A prognostic study of associations between post-operative test results
and subsequent bleeding

List of abbreviations

Acronym	Details
AKI	Acute kidney injury
AUC	Area under the curve
CCB	Clinical concern about bleeding
CI	Confidence interval
CICU	Cardiac intensive care unit
CNS	Central nervous system
CPAP	Continuous positive airway pressure
CRF	Case report form
CTEU	Clinical Trials and Evaluation Unit
eGFR	estimated Glomerular Filtration Rate
EPT	Early pro-haemostatic treatment
ETP	Endogenous thrombin potential
FBC	Full blood count
GI	Gastrointestinal
HArVeST	A Randomised Controlled Trial to Assess the Extent of Intimal Hyperplasia and Atherogenesis in Bypass Vein Grafts Following Different Surgical Preparation Techniques
HB	Haemoglobin
HCT	Haematocrit
IPF	Immature platelet fraction
IQR	Inter quartile range
MI	Myocardial infarction
MPV	Mean platelet volume
NSTS	NHS Strategic Tracing Service
OR	Odds ratio
PASPORT	Patient-specific cerebral oxygenation monitoring as part of an algorithm to reduce transfusion during heart valve surgery: a randomised controlled trial
PATS	Patient Analysis and Tracking Systems
ProMPT	Propofol cardioplegia for Myocardial Protection Trial
PROTECTION1	Pulmonary protection with low frequency ventilation during cardiopulmonary bypass: a prospective randomised study
RBC	Red blood cells
rFVII	Recombinant human coagulation factors VII
ROTEM	Point-of-care whole blood haemostasis analyser
SAP	Statistical analysis plan
SD	Standard deviation
STROBE	STrengthening the Reporting of OBservational studies in Epidemiology
TEG	Thromboelastogram
TITRe2	A multi-centre randomised controlled trial of Transfusion Indication Threshold Reduction on transfusion rates, morbidity and healthcare resource use following cardiac surgery
UHBristol	University Hospitals Bristol NHS Foundation Trust

STATISTICAL ANALYSIS PLAN

COPTIC: Coagulation and platelet laboratory testing in cardiac surgery
A prognostic study of associations between post-operative test results and subsequent bleeding

Acronym	Details
VeRDICT	Preoperative Volume Replacement vs. usual care in Diabetic patients having CABG surgery: a randomised controlled Trial
WBC	White blood cells

Definitions

Coagulopathy

Any abnormality of blood clotting (coagulation factors or platelets)

Clinical concern about bleeding

Excessive actual blood loss or non-routine pro-haemostatic intervention before excessive blood loss has occurred or coagulopathic bleeding identified at re-operation.

P2Y₁₂ blocker

Clopidogrel or Prasugrel

Post-operative test results

Laboratory test results from Multiplate, ROTEM or TEG

1. INTRODUCTION

1.1 Scope

This statistical analysis plan (SAP) covers the analyses of the Multiplate, ROTEM and TEG results for the post-operative blood samples collected for the COPTIC study (part of Study B). This SAP does not cover the Health Economics analyses which will be covered in separate documentation.

Any changes made to this SAP after approval must be clearly justified and documented as an amendment at the end of this document. The SAP should then be re-approved.

1.2 SAP document approval

The study statistician should authorise the SAP.

1.3 Skeleton tables and figures

Throughout this document references are made to any skeleton tables and figures to be used in the reporting of the study (e.g. **Figure F1** or **Table T1**). Such tables and figures can be found in **Appendix A** of this document, and are intended as a guide for study reporting. Final versions of the tables/figures may differ: tables may be combined, and/or their layout or numbering may differ. However the content should be consistent with **Appendix A**.

2. STUDY BACKGROUND AND OBJECTIVES

2.1 COPTIC study background

Cardiac surgery is associated with complex abnormalities in the blood coagulation (clotting factors and platelets) that are caused by patients' characteristics, drug treatments and the mechanical interventions that are necessary for surgery. These include pre-operative abnormalities such as low platelet function caused by exposure to anti-platelet drugs, and intra-operative abnormalities such as dilution or inactivation of blood clotting factors and platelets, reduced clotting factor function because of heparin and increased clot breakdown. The combination of pre-operative and intra-operative abnormalities in blood coagulation may lead to increased bleeding after cardiac surgery that requires treatment with blood components (e.g. fresh frozen plasma, platelet transfusion) and/or red cell transfusion. Bleeding, blood component and red cell transfusion are independently associated with adverse clinical outcomes after cardiac surgery.

The COPTIC study will investigate how the results of improved testing for abnormalities in blood coagulation abnormalities both before surgery (COPTIC Study A) and after surgery (COPTIC Study B) can be used to benefit patients by improving diagnosis and appropriate treatment with blood components.

2.2 Overview of COPTIC study design

COPTIC is a prospective observational study of patients undergoing cardiac surgery at the Bristol Heart Institute.

- i. All participants undergo standard pre-operative, anaesthetic, surgical and post-operative care according to existing protocols.
- ii. Blood samples are obtained in the operating theatre at the following time-points:

STATISTICAL ANALYSIS PLAN

[figure not shown]
COPTIC: Coagulation and platelet laboratory testing in cardiac surgery
A prognostic study of associations between post-operative test results and subsequent bleeding

- a. Immediately before induction of anaesthesia (*pre-operative sample; 9.5mls*)
- b. Immediately after reversal of heparin anticoagulation (*post-operative sample; 18.5mls*)

Data are collected until 12 hours after admission to Cardiac intensive care unit (CICU). The study timings are shown in Figure 1.

Figure 1: Timeline for COPTIC study

T0: time of pre-op sample

T1: cessation of CPB

T2: administration of final routine dose of protamine

T3: time of post-op sample

T4: time of arrival in CICU

T5: 6 hours after arrival in CICU

T6: 12 hours after arrival in CICU

T7: CICU discharge

Interval 1 time interval between pre-op and post-op samples [T3-T0]

Interval 2a post-op sample to 6 hours after admission to CICU [T5-T3]

Interval 2b post-op sample to 12 hours after admission to CICU [T6-T3]

Interval 2 time interval between post-op sample and CICU discharge [T7-T3]

This SAP refers to the analysis of post-operative Multiplate test results, ROTEM test results and TEG test results (part of Study B). A separate analysis plan will be written for the analyses of the other laboratory results from post-operative samples (also Study B).

2.3 Study objectives

COPTIC Study B examines the relationship between post-operative abnormalities in blood coagulation and 'clinical concern about bleeding' (CCB) after cardiac surgery (see section 5.1 for the definition of the primary outcome). Although numerous abnormalities in both clotting factors and platelets have been reported in patients before cardiac surgery, the most prevalent and clinically important abnormalities are likely to be in platelets. This is because anti-platelet drugs such as aspirin and the P2Y₁₂ blockers, clopidogrel or

STATISTICAL ANALYSIS PLAN

COPTIC: Coagulation and platelet laboratory testing in cardiac surgery
A prognostic study of associations between post-operative test results
and subsequent bleeding

prasugrel, are prescribed widely to patients before cardiac surgery and markedly reduce platelet function.

Approximately 50% of cardiac surgery patients receive aspirin alone up to the day of surgery and approximately 25% receive dual therapy with aspirin plus a P2Y₁₂ blocker. For the dual-therapy sub-group, current practice guidelines suggest withdrawal of the P2Y₁₂ blocker approximately 5 days before cardiac surgery but continuation of aspirin up to the day of surgery. In practice, the duration of withdrawal varies between 0 and 7 days because of clinical operational constraints. We hypothesise that exposure to aspirin alone or exposure to aspirin + P2Y₁₂ blocker is associated with more CCB than no exposure to anti-platelet drugs. We also hypothesise that in the dual-therapy sub-group, a short time of withdrawal of P2Y₁₂ blocker is associated with more CCB than a long time of withdrawal.

It is already known that anti-platelet drugs cause abnormal results in some laboratory tests of platelet function. Some other factors may also influence platelet function tests. It is unknown whether any laboratory test or combination of tests of platelet function can be used to predict CCB. The overall aim of the COPTIC Study B is to estimate the association between the results from a panel of laboratory tests of platelet function and count performed after cardiac surgery and CCB in all patients. Since anti-platelet drugs have marked effect of some platelet laboratory tests, we will also estimate the association between test results and CCB in patient subgroups (no anti-platelet drugs vs. aspirin alone vs. aspirin plus P2Y₁₂ blockers). We will also estimate the association between test results and duration of withdrawal of P2Y₁₂ blockers and the relationship between duration of withdrawal of P2Y₁₂ blockers and CCB. Other pre-operative, intra-operative and post-operative factors (up to T6) will be considered as potential confounders of the association between platelet test results and CCB. Estimates of association will be used to generate a parsimonious predictive model of the probability of CCB based on post-operative platelet test results and other factors.

The specific study objectives are as follows:

1. In all patients:
 - (a) to describe the distributions of post-operative test results ('primary predictors' and 'secondary predictors', see [section 2.6](#)).
 - (b) to examine the relationship between post-operative test results and the primary clinical outcome of CCB (see [section 5.1](#)).
2. In the patient sub-groups *no anti-platelet drugs, aspirin alone* and *aspirin+ P2Y₁₂ blockers*:
 - (a) to describe the distributions of post-operative test results ('primary predictors' and 'secondary predictors')
 - (b) to examine the relationship between i) post-operative test results and ii) the primary clinical outcome of CCB (see [section 5.1](#)).
3. In the patient sub-group *aspirin+ P2Y₁₂ blockers*:
 - (a) to describe the distributions of duration of withdrawal of P2Y₁₂ blocker

STATISTICAL ANALYSIS PLAN

COPTIC: Coagulation and platelet laboratory testing in cardiac surgery
A prognostic study of associations between post-operative test results and subsequent bleeding

(b) to examine the relationship between the duration of withdrawal of P2Y₁₂ blocker and post-operative test results.

(c) to examine the relationship between the duration of withdrawal of P2Y₁₂ blocker and the primary clinical outcome of CCB.

2.4 Primary outcome

The primary outcome for COPTIC Study B is clinical concern about bleeding (CCB; see section 5.1 for the definition).

2.5 Secondary outcomes

Secondary outcomes for COPTIC Study B are:

(a) Whether red cell transfusion was given and the quantity of red cells transfused.

(b) The quantities of non-routine pro-haemostatic treatments (see [section 5.2](#) for the definition).

(c) Serious post-operative complications (see [section 5.2](#) for definition).

2.6 Laboratory predictors

Although approximately 30 post-operative test results have been recorded in the COPTIC Study B, these may be sub-classified according to likelihood of an association with the primary outcome of CCB (objectives 1 and 2):

2.6.1 Primary laboratory predictors (test results considered likely to predict CCB)

Test result	Laboratory test and platform	Likely predictor of CCB
Platelet count	FBC (XE-2100 cell counter)	LOW test result
Multiplate ADP test AUC	Multiplate	LOW test result
Multiplate AA test AUC	Multiplate	LOW test result
Multiplate TRAP test AUC	Multiplate	LOW test result
Multiplate ADR test AUC	Multiplate	LOW test result
ROTEM intem CT	ROTEM	HIGH test result
ROTEM intem alpha	ROTEM	LOW test result
ROTEM intem mcf	ROTEM	LOW test result
ROTEM intem ml	ROTEM	HIGH test result
ROTEM intem maxV	ROTEM	LOW test result
ROTEM intem maxV-t	ROTEM	HIGH test result
ROTEM extem CT	ROTEM	HIGH test result
ROTEM extem alpha	ROTEM	LOW test result
ROTEM extem mcf	ROTEM	LOW test result

STATISTICAL ANALYSIS PLAN

COPTIC: Coagulation and platelet laboratory testing in cardiac surgery
A prognostic study of associations between post-operative test results and subsequent bleeding

ROTEM extem ml	ROTEM	HIGH test result
ROTEM extem a10	ROTEM	LOW test result
ROTEM extem maxV	ROTEM	LOW test result
ROTEM extem maxV-t	ROTEM	HIGH test result
ROTEM fibtem mcf	ROTEM	LOW test result
ROTEM fibtem a10	ROTEM	LOW test result
ROTEM extem mcf - fibtem mcf	ROTEM	LOW test result
ROTEM intem CT - heptem CT	ROTEM	HIGH test result
TEG CK rmin	TEG	HIGH test result
TEG CK angledeg	TEG	LOW test result
TEG CK ma	TEG	LOW test result
TEG CK ly60	TEG	HIGH test result
TEG CK rmin – CKH rmin	TEG	HIGH test result

2.6.2 Secondary laboratory predictors (test results considered less likely to predict CCB)

Test result	Laboratory test and platform	Likely predictor of CCB
Haemoglobin concentration (HB)	FBC (XE-2100 cell counter)	LOW test result
Haematocrit (HCT)	FBC (XE-2100 cell counter)	LOW test result
White blood cells (WBC)	FBC (XE-2100 cell counter)	LOW test result
Absolute neutrophils	FBC (XE-2100 cell counter)	LOW test result
Mean platelet volume (MPV)	FBC (XE-2100 cell counter)	HIGH or LOW test result
Mean platelet volume (MPV) x Platelet count	FBC (XE-2100 cell counter)	LOW test result
Immature platelet fraction (IPF)	FBC (XE-2100 cell counter)	HIGH or LOW test result
Absolute reticulocytes (RETICS)	FBC (XE-2100 cell counter)	HIGH or LOW test result
Multiplate ADP test velocity	Multiplate	LOW test result
Multiplate ADP test amplitude	Multiplate	LOW test result
Multiplate AA test velocity	Multiplate	LOW test result
Multiplate AA test amplitude	Multiplate	LOW test result

STATISTICAL ANALYSIS PLAN

COPTIC: Coagulation and platelet laboratory testing in cardiac surgery
A prognostic study of associations between post-operative test results and subsequent bleeding

Multiplate TRAP test velocity	Multiplate	LOW test result
Multiplate TRAP test amplitude	Multiplate	LOW test result
Multiplate ADR test velocity	Multiplate	LOW test result
Multiplate ADR test amplitude	Multiplate	LOW test result

2.6.3 Laboratory predictors: timings of test parameters

For each platform, test results have been classified as relevant to a 'rapid' or 'standard' time frame:

Standard Test result	'Early phase' alternative
Multiplate ADP test AUC	ADP test velocity
Multiplate AA test AUC	AA test velocity
Multiplate TRAP test AUC	TRAP test velocity
Multiplate ADR test AUC	ADR test velocity
ROTEM intem CT	n/a
ROTEM intem alpha	n/a
ROTEM intem mcf	Intem A5 or A10
ROTEM intem ml	n/a
ROTEM intem maxV	n/a
ROTEM intem maxV-t	n/a
ROTEM extem CT	n/a
ROTEM extem alpha	n/a
ROTEM extem mcf	Extem A5 or A10
ROTEM extem ml	n/a
ROTEM extem maxV	n/a
ROTEM extem maxV-t	n/a
ROTEM fibtem mcf	Fibtem A5 or A10
ROTEM extem mcf - fibtem mcf	Extem A5-Fibtem A5; Extem A10-Fibtem A10
ROTEM intem CT - heptem CT	n/a
TEG CK rmin	n/a
TEG CK angledeg	n/a
TEG CK ma	CK A30
TEG CK ly60	n/a
TEG CK rmin – CKH rmin	n/a

STATISTICAL ANALYSIS PLAN

COPTIC: Coagulation and platelet laboratory testing in cardiac surgery
A prognostic study of associations between post-operative test results and subsequent bleeding

All other post-operative FBC, Multiplate, ROTEM and TEG test results are considered unlikely to predict CCB.

2.7 Other predictors and confounders

The role of other possible predictors and potential confounders will be investigated. These factors will be evaluated for association with the laboratory test results and association with the primary and secondary outcomes and will include age, sex, diabetes, type of surgery, operation urgency, pre-operative kidney function (estimated Glomerular Filtration Rate; eGFR) and pre-operative HCT. Post-operative platelet count will also be included in all models.

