7.2 Specific analysis procedure

The approach is to evaluate the separate platforms (Multiplate/preop; ROTEM; TEG; Multiplate/postop) individually in the first instance, and then evaluate whether the inclusion of additional platforms would improve this. The reason for considering groups of variables by platform (rather than simply choosing the 'best' subset of variables) is because there is no cost of using extra variables from one platform, but an extra cost of doing a second test. The specific steps are as follows:

- Step 1 Review the prediction achieved by patient characteristics. Define an optimal model based only on "baseline" covariates⁶. There will be a separate model for
- **any CCB** (intra-operative or post-operative) and
 - **post-op CCB** only
- Comment: We expect these models to be consistent with one another, not least because the majority of events (post-op CCPB events) will be common to both models.*
- Step 2 Review of each test platform to obtain the best model for each, including the baseline covariates:
- pre-operative Multiplate in relation to **any CCB** (this model is interesting in its own right, but from a slightly different perspective, i.e. it allows the care team to make a plan to mitigate the risk of CCB or to prepare to manage it)
 - pre-operative Multiplate in relation to **post-op CCB**
 - post-operative Multiplate in relation to **post-op CCB**
 - post-operative ROTEM in relation to **post-op CCB**
 - post-operative TEG in relation to **post-op CCB**
- Comment: Each of these models will consider all variables for the test/timepoint, i.e. consider the test/timepoint as a "package." The first model stands alone for **any CCB**. For **post-op CCB**, this step will identify which of the latter four models is the best platform for predicting CCB, i.e. provides the best prediction. We hypothesise that the best platform will be one of the post-op platforms because the information from these is more 'proximal' to the outcome for these models, i.e. **post-op CCB**.*
- For the best test/timepoint** (assuming there is one best test), we will also investigate whether a model using test variables that are available early (for the test identified as best) performs as well as a model using the standard test variables available at "test completion."

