7.3 Model fitting

Models will be fitted first for the standard time frame. Then, models will be fitted for the rapid time frame (see [Table 2.6.3](#)), testing whether this results in a “significant” deterioration in prediction. Comparing rapid and standard time frames is interesting because there may be a trade-off between potential benefits of earlier decision making (e.g. allows definitive treatment to be provided more quickly, thereby preventing blood loss) vs. potential harms (e.g. somewhat less good prediction).

The contribution of all of these baseline characteristics to the prediction of CCB were incorporated into a single score which was forced into models of laboratory predictors with a coefficient of 1.00 in order to enable comparisons between different models based on the various laboratory test platforms.

All laboratory measures from a platform were included for each model, with multivariable fractional polynomial techniques used to investigate the linearity of terms. All transformations and centering found to improve the fit of the models were implemented. Backward elimination was undertaken to select the final models with a threshold of inclusion of 0.05 and exclusion of 0.10. Initial models only considered the standard test results (see Table 2); subsequently the ‘early phase’ alternatives were considered for any terms that significantly contributed to the model.

The following models were constructed:

- **Model 2A:** pre-operative Multiplate in relation to **any CCB**
- **Model 2B:** pre-operative Multiplate in relation to **post-op CCB**
- **Model 2C:** post-operative Multiplate in relation to **post-op CCB**
- **Model 2D:** post-operative ROTEM in relation to **post-op CCB**
- **Model 2E:** post-operative TEG in relation to **post-op CCB**

Each model was then compared to a baseline model containing only the baseline characteristics in order to evaluate the contribution of the selected laboratory test results to the prediction of CCB. These are presented as receiver operating characteristic (ROC) curves.

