7.4.2 Adjustment in models

The intention is to adjust all models for potential confounders (see [section 2.7](#))⁷. These will be identified as either by significantly contributing to multivariate models, with likelihood ratio p-value of <0.05, or by modifying the effect estimate by greater than 10%. Age and sex will be entered in all final models, regardless of individual statistical contribution.

Evidence of effect modification will be investigated, by fitting interaction terms into the statistical models and consideration of the effect on the fitted estimates.

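### Section 2.7 puts the post-operative platelet count in every model, including the baseline and pre-operative models, where it is not yet available and where footnote 6 leaves it out

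*SAP*

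**What the plan says.** Section 2.7 lists the potential confounders (age, sex, diabetes, surgery type, urgency, eGFR, pre-operative haematocrit) and ends with an unqualified rule: "Post-operative platelet count will also be included in all models". Section 2.2 fixes when that count is taken ("T3: time of post-op sample"), which is after reversal of heparin.

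The models are set out in sections 7.2 and 7.3. Step 1 fits models on baseline covariates alone, one for any CCB, glossed as "intra-operative or post-operative", and one for post-op CCB. Footnote 6 enumerates those covariates. The post-operative platelet count is not among them. Step 2 adds the platforms, beginning with "Model 2A: pre-operative Multiplate in relation to any CCB". Section 7.2 gives the reason for that model: "it allows the care team to make a plan to mitigate the risk of CCB or to prepare to manage it". Model 2B uses the same pre-operative test for post-op CCB. Models 2C to 2E use the post-operative platforms.

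On evaluation, section 7.3 says: "Each model was then compared to a baseline model containing only the baseline characteristics". Section 7.4.2 says "The intention is to adjust all models for potential confounders" and refers back to section 2.7, but the only variables it forces into the final models are age and sex.

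**The concern.** A prediction model can use only what is known when the prediction is made. Followed literally, section 2.7 puts a value measured at the end of the operation into models that describe risk before it. Model 2A would then not serve its stated purpose, and Model 2B would no longer show what pre-operative information alone achieves. For the any-CCB outcome there is a further difficulty of order: where the qualifying event happens before T3, the covariate is measured after the outcome.

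The SAP also gives two different answers on model content. One analyst following section 2.7 and another following footnote 6 would fit different Step 1 models, and so different baseline scores. Every later comparison rests on that score. If the two passages are each applied in part, so that the count is in the platform model but not in the comparator, a full blood count result is counted as part of what Multiplate, ROTEM or TEG adds.

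**Working it through.** The SAP states no figure on this point, so the check sets the timing and the model content side by side.

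**1. When the count exists.** It is measured at T3. Interval 1 runs from T0 to T3, so anything in interval 1 precedes the count.

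**2. Where section 2.7 places it, against what each model is for.**

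| Model | Outcome | Information the model is meant to use | Effect of adding the T3 count |
|---|---|---|---|
| Step 1 | any CCB | baseline covariates only | not available at baseline; follows any event before T3 |
| Step 1 | post-op CCB | baseline covariates only | not available at baseline; precedes the outcome |
| 2A | any CCB | baseline plus pre-operative Multiplate | not available for planning; follows any event before T3 |
| 2B | post-op CCB | baseline plus pre-operative Multiplate | not available before surgery; precedes the outcome |
| 2C to 2E | post-op CCB | baseline plus a post-operative platform | available and in the right order |

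The availability problem therefore affects four models. The reversed order affects two, and only for events before T3.

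**3. Which CCB events can precede T3.** Section 5.1 places the early pro-haemostatic treatments in interval 2b (T3 to T6) and judges drain loss at T5. Section 6.1 uses interval 2 for these treatments but allows interval 1 or interval 2b for therapeutic protamine. So within the CCB definition, therapeutic protamine in interval 1 is the one component expressly dated before T3. Section 7.2 adds intra-operative events to any CCB without giving them a window, and theatre time between T3 and T4 falls after the sample.

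**4. What the other passages say about content.** Step 1 admits baseline covariates only. Footnote 6 lists a pre-operative platelet function measure and no post-operative count. Section 7.1 names the pre-operative platelet count as an expected predictor. None of these agrees with a T3 count in every model, and nothing in sections 7.2 to 7.4 limits the section 2.7 sentence.

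**5. The comparator for Models 2C to 2E.** Section 2.6.1 assigns the platelet count to the full blood count analyser, not to any of the three platforms. There are three ways to read the text:

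- Section 2.7 governs both models. The count is in both, and the difference is the platform's own.
- Footnote 6 and section 7.3 govern both models. The count is in neither, and the difference is again the platform's own.
- Section 2.7 governs the platform model and footnote 6 the comparator. The difference is the platform's gain plus the count's gain.

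Only the third reading miscredits the count.

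**6. Illustration of the third reading, on assumed inputs.** None of these inputs is in the SAP: 20% CCB, a standard normal baseline score with log odds ratio 0.6 per SD, an independent standard normal platelet count, a platform with no information, and 400,000 simulated patients.

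| Platelet count OR per SD | AUC, baseline only | AUC, baseline plus count | Gain |
|---|---|---|---|
| 0.8 | 0.659 | 0.670 | 0.01 |
| 0.7 | 0.657 | 0.682 | 0.025 |
| 0.6 | 0.654 | 0.702 | 0.048 |

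Here the whole gain would be credited to a platform that adds nothing. This is the extreme case. A platform already correlated with the count would leave less to miscredit.

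**The case against.** The best defence is that the specific procedure overrides the general sentence. Section 7.3 builds each model from a single baseline score with its coefficient fixed at 1.00 plus the platform's own measurements, and the count is in neither. Section 1.1 scopes the SAP to post-operative samples, and the amendment log records that the approach joining pre- and post-operative analyses came in with version 3.0. Section 2.7 may well be general text about post-operative tests that was never reconciled. That is a plausible account of how the conflict arose. It does not settle it, because the sentence is current and carries no exception.

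Other parts of the defence stand and limit the point:

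- Section 7.4.2 refers to section 2.7 but does not repeat the forced inclusion of the count. It selects confounders by p-value or by change in the estimate.
- A reader might infer that platelets transfused as part of a CCB event raise the T3 count. The documents do not establish this. Platelet transfusion in interval 1 appears only in a secondary endpoint in section 6.2, and the explanatory bracket there describes a window starting at the post-operative sample.
- A reader might infer that every platform's gain is inflated. That needs the third reading in the working. Under either consistent reading it does not occur.

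**Conclusion.** The point holds as an error in a stated rule with a cheap remedy. Applied as written, section 2.7 puts a measurement that does not yet exist into both Step 1 models and Models 2A and 2B, and it contradicts the baseline-only wording of Step 1 and footnote 6. For Model 2A the availability problem is enough by itself, however many events precede T3. The reversed order is a smaller matter, confined to the any-CCB models and to events before T3.

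The miscrediting in Models 2C to 2E is conditional on section 2.7 governing the platform model and footnote 6 its comparator. Its size cannot be derived from the SAP. The illustrative AUC gains of about 0.01 to 0.05 rest wholly on assumed inputs and a platform with no information, so they are not an estimate for this study. The stronger conclusion, that the main answer is biased in favour of all platforms, is not supported.

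**What to change.** Replace the last sentence of section 2.7 with wording to this effect: the post-operative platelet count is used only in models of post-operative tests against post-op CCB (Models 2C to 2E and the Step 3 and 4 models built on them). The Step 1 models and Models 2A and 2B use only covariates available before surgery, as listed in footnote 6.

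Where the T3 count enters Models 2C to 2E, put it in the comparator as well, or report that comparator in addition to the baseline-only one, so that the gain shown is the platform's own. State whether the count has a freely estimated coefficient or sits inside the fixed-coefficient score. Bring footnote 6 and section 7.4.2 into line with the new sentence. The windows for CCB events in sections 5.1, 6.1 and 7.2 also need to be reconciled, so that it is clear which events precede T3.

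The cost is SAP wording and one extra comparator model. The reported AUC gain of each platform may be slightly smaller. Because Model 2B will not carry the count, the Step 2 ranking of 2B against 2C to 2E should say so.
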